6.3 MEASURES TO MINIMIZE BIAS: RANDOMIZATION AND BLINDING

Protocol Number: 21-0640

February 1, 2022

Randomization: A randomization schema will be pre-generated by the Biostatistics Unit at FIMR, using the Biostatistics Randomization Management System (BRMS) software, by a statistician not affiliated with the study. Responders will be randomly assigned in a 2:1 ratio to either taVNS or sham and given a unique randomization ID number. The randomization schema will be read into the randomization module in REDCap, a data management system that only the coordinator can access. The software will monitor the allocation progress and responder assignment.

Concealed Allocation: The coordinator will create and keep a crosswalk between participant ID, unique randomization ID number, and assignment in REDCap. Nesos Corp will use the unique randomization ID number to label the molds for fitting the device. After the fitted devices are received, the coordinator will give Nesos Corp a table with unique randomization ID number labels and assignment for Nesos Corp to designate the appropriate program to the device based on the responder's allocation. For the taVNS program, when the responder uses the app to activate the device, the taVNS will provide stimulation at a value that was calibrated to that responder. For the sham program, the device will not provide any electrical stimulation.

Blinding: Responders in the taVNS and the sham group will be blinded to their assignment. *Both groups will not be able to detect the stimulation provided* and thus, will not know which group they are in. The directions provided and the use of the application will be the same for both groups. All investigators will be blinded to participation assignment as well. Biologic outcome measures will be conducted by [name]. The CAPS will be conducted by senior study staff and oversight of self-report survey completion will be provided by the research coordinator. Only the research coordinators will not be blinded to the assignment. They will receive the allocation assignment after enrollment and will coordinate with Nesos Corp to program the devices corresponding to assignment.

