6.4 STUDY INTERVENTION COMPLIANCE

In order to verify compliance with the study procedures, the completion of case report forms is required for each study visit for participants. These records will be periodically reviewed investigator(s) to ensure all study procedures were adequately performed. In addition, investigator(s) will cross reference the documented information against the randomization schema to ensure participants were appropriately randomized and administered the procedures as specified.

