7.2 PARTICIPANT DISCONTINUATION/WITHDRAWAL FROM THE STUDY

Given that participation in this study is voluntary, participants may elect to withdraw at any time by notifying a researcher. It is also possible that participation in this study may end without the participant's consent. This decision may be made by a researcher, the Northwell Health Human Research Protection Program, or a federal or state regulatory agency.

Reasons for withdrawal may include: failure to comply with study requirements; failure to keep study appointments; a change in their medical history, medications, or lifestyle (including alcohol, tobacco, or substance usage) that results in them no longer meeting study eligibility; inability to tolerate study procedures; it is not in the participant's best interest to continue on this study; or the study is stopped.

Participants that prematurely withdraw from the study due to an adverse event will be followed (e.g. telephone contact, follow-up visits, etc.) until resolution of the event or they indicate they no longer want to be contacted. In addition, a designated investigator will have access to treatment status at all times and provide that information to appropriate medical personnel in the event of medical emergencies. If the participant withdraws from this study or if s/he is withdrawn from the study, any data already collected will continue to be used, but no new data will be collected. The reason for participant discontinuation or withdrawal from the study will be recorded.

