10.1.7 QUALITY ASSURANCE AND QUALITY CONTROL

The principal investigator and team will perform internal quality management audits of study conduct, data and biological sample collection, and documentation completion will be performed by the principal investigator. In addition, she will cross reference the documented information with information stored in the randomization portal to ensure participants were appropriately randomized and administered the procedures as specified.

In the event of an audit, the study team will provide direct access to all trial related documents and reports for the purpose of monitoring and auditing by the Northwell Health Human Research Protection Program and/or federal and state regulatory agencies.

Aims 1 & 2: Data verification will be performed by someone other than the individual originally collecting the data, or by double entry. A statement reflecting the results of the ongoing data review will be incorporated into the annual report for the independent monitor.

Aim 1: Focus groups will be recorded on 2 audio recorders so that there is a back-up recorder should there be any difficulties. The focus group will follow a discussion guide that is developed and approved by the study team. Only a FIMR-approved transcription service that is HIPAA-compliant will be used for focus group audio file transcription.

Aim 2: The contact PI, [name] is responsible for oversight and monitoring of the data, assuring protocol compliance, and conducting the safety reviews after 5 participants or at bi-monthly meetings, whichever comes first or more frequently, if needed. The project coordinator will also be responsible for day-to-day oversight of research, and ensuring the integrity and

Protocol Number: 21-0640

February 1, 2022

privacy of the data. Additionally, [name] will act as an independent data monitor and will be included in all correspondence.

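### Section 6.3 blinds all investigators, but 6.4 and 10.1.7 have investigators check records against the randomization schema, with no masking or deferral of that check

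*Protocol*

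**What the plan says.** Protocol 6.3 sets the blinding rule. Participants are blinded, and for staff: "All investigators will be blinded to participation assignment as well". The exception is narrow: "Only the research coordinators will not be blinded to the assignment". The schema is loaded into the REDCap randomization module, with REDCap described as "a data management system that only the coordinator can access". The link to arm sits with the same role: "The coordinator will create and keep a crosswalk between participant ID, unique randomization ID number, and assignment in REDCap".

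Two later sections give investigators a task that uses this information. In 6.4, "investigator(s) will cross reference the documented information against the randomization schema". In 10.1.7, of the principal investigator, "she will cross reference the documented information with information stored in the randomization portal". Both give the same purpose: to verify that people were allocated correctly and received what was specified for them.

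On calibration, 6.1.2 determines a perceptual threshold in every participant by applying short trains of stimulation and asking whether they were felt. Section 6.1.1 has a researcher calibrate the level for each responder around the baseline visit. Section 4.3 says the sham arm gets no current, 2.2 that the sham device is unable to stimulate, and 6.3 that the sham program delivers nothing.

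**The concern.** A randomization schema maps an ID to an arm. Someone who opens it to verify that a participant was handled according to allocation sees the arm, unless the list is masked. Section 6.3 says investigators do not have that knowledge and that access is limited to the coordinator; 6.4 and 10.1.7 direct investigators to use it.

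Section 4.1 justifies the double-blind design as a protection against bias from participants and investigators, and says the pilot should reproduce the method of the later trial. If the pilot's own quality check opens the blind, that part of the method has not been piloted. The outcome most open to a rater's knowledge is the CAPS interview at 8 weeks. Section 8.1 uses estimates from this and the other tertiary measures to calculate effect sizes for the larger RCT.

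Calibration raises a related, weaker question. If the threshold search were run on a device already carrying the sham program, the answers could suggest the arm to the researcher doing it.

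**Working it through.** No sample-size, power or precision figure is involved, so the check sets the sections side by side.

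**Allocation check**

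1. *Who may know the arm.* 6.3: coordinators only; investigators blinded.
2. *Who holds the information.* 6.3: the coordinator keeps the crosswalk and has sole access to the system. 10.1.6 likewise gives only the project coordinator the key linking identity to random ID.
3. *Who performs the check.* 6.4: investigators, against the schema. 10.1.7: the principal investigator, against the portal.
4. *What the check needs.* Verifying that the allocated procedure was delivered requires the allocation, or a masked substitute for it. Neither section describes a masked substitute.
5. *When it happens.* Not stated. In 6.4 it follows a sentence on periodic review of case report forms, and in 10.1.7 it stands beside internal audits of study conduct. A check during the trial is the natural reading, but the text does not fix it.
6. *How much it covers.* No sampling limit is given, so it could extend to all 30 participants. Under 2:1 the expected split is 30 × 2/3 = 20 taVNS and 30 × 1/3 = 10 sham. This is expected only, because 6.3 states a ratio and no blocking.

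Steps 1 and 2 conflict with step 3 unless step 4 is masked or step 5 falls after follow-up. The protocol provides for neither.

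**Calibration**

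1. 6.1.2: threshold found in every participant by delivering stimulation.
2. 4.3: no current for the sham arm, with no exception. 2.2 and 6.3: the sham device or program gives none.
3. 6.3: programs are designated after the fitted devices arrive. 6.1.1: calibration, hand-over of the ID-matched device and the first supervised session all belong to the baseline-visit procedure. Whether calibration comes before loading of the allocated program is not said, nor which device or program is used.
4. Two readings follow. If live current is used before the sham program is loaded, 6.1.2 and 6.3 agree and the absolute sentence in 4.3 needs qualifying. If the sham-programmed device is used, the trains in 6.1.2 deliver nothing to sham participants and their answers could hint at the arm.

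The text does not settle which reading applies.

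**The case against.** The strongest reply is that the sections can be made compatible. The timing of the check is not stated, and in 6.4 the word for periodic review governs the case report forms, not the schema comparison. A check after follow-up, or one confined to randomization IDs and device labels, would unblind nobody while outcomes are being collected. Coordinator-only access cannot be literal for REDCap as a whole either, since 10.1.6 has responders enter surveys in it and 10.1.8.1 gives necessary research staff access. This stands to the extent that unblinding is a risk of following the text and not a certainty. It does not remove the problem, because a harmless version of the check has to be supplied by the reader.

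Materiality is also limited. The primary outcomes are feasibility proportions, no between-arm test is described, and 8.1 and 9.3.1 already urge caution with the effect sizes. That is accepted, and it limits the weight of the point.

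Some stronger inferences are tempting but not supported:

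- *That 7.2 is a further contradiction.* Its wording is: "designated investigator will have access to treatment status at all times and provide that information to appropriate medical personnel in the event of medical emergencies". That is an emergency route, not routine unblinding.
- *That the device company's knowledge breaks the blind.* 6.3 discloses it: "After the fitted devices are received, the coordinator will give Nesos Corp a table with unique randomization ID number labels and assignment". The coordinator-only sentence reads naturally as being about study staff.
- *That calibration reveals the arm.* Live threshold-finding before the program is loaded is a workable reading. Even on a sham-programmed device, a participant told that sensation may or may not occur could report feeling something, so the arm could not be read off with certainty.
- *That self-report scales are safe unless participants guess their arm.* 6.3 has the research coordinator, who is unblinded, oversee survey completion, so that reassurance cannot be given.
- *That the person checking or calibrating also rates the CAPS.* Names are removed, so overlap can be neither asserted nor excluded.

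**Conclusion.** The contradiction between 6.3 on one side and 6.4 and 10.1.7 on the other is real, and confidence in it is high. Performed during the trial as written, the check can disclose assignments to investigators, with up to all 30 in scope. This rests on two readings: that the schema or portal shows the arm, and that the check is neither masked nor deferred, since no section says it is. The consequence falls on the CAPS and other tertiary between-arm estimates and on the claim to have piloted a double-blind method, not on the primary feasibility proportions. The size of any bias cannot be estimated from the document.

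The calibration point is a request to reconcile, with lower confidence. An unstated order of steps and an unqualified sentence in 4.3 leave two readings open, and the documents do not show that calibration unblinds anyone.

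**What to change.** **Allocation check.** In 6.4 and 10.1.7, reassign it by one of these routes:

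- The Biostatistics Unit statistician who generates the schema and is not affiliated with the study, reporting only match or mismatch to investigators. This is the most independent route. That person would need the coordinator's crosswalk, the relevant study records and the device-programming records, so it is more than a comparison of two lists.
- The already unblinded coordinator, with the same restricted reporting. This is simpler but less independent, because the coordinator created the crosswalk.
- The investigators themselves, but only after the last 8-week visit. Allocation errors would then be found too late to correct.

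**Calibration.** Reconcile 2.2, 4.3, 6.1.1, 6.1.2 and 6.3 on which device or program is used for sham participants and whether the step precedes loading of the allocated program, and arrange it so that it does not reveal the arm to anyone assessing outcomes. Which stimulation rule applies is for the study team.

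**Cost.** Protocol wording and some of one person's time for the allocation check. For calibration, wording only if it already precedes loading; otherwise a change in the order of the step or in who performs it. Sample size, visits and outcome measures are unchanged.

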The Research Data Capture application, REDCap, a secure, HIPAA-compliant, web-based tool, will be used to create instruments for eligibility and recruitment tracking, survey questionnaires, and biological assessments. This application is accessible via the web through a secure login. Survey questionnaire responses will be entered directly into REDCap by responders from laptops or tablets provided at each visit. Tracking and biological measures will be entered into REDCap by the project coordinator after each visit. Usage data from the taVNS wearable devices will be extracted from the cloud by Nesos Corp and transferred to the study team following institutional secure data protocols after 8 weeks. Usage data will be stored in a locked, electronic folder on a secure, HIPAA-compliant institutional server, accessible only to those approved to be part of the study by our IRB. Data quality will be monitored by built-in validation checks in REDCap, such as bounds on numeric data, inclusion criteria flags, and missing data flags.

Adverse Events (AE)

Aim 1 & 2: As per FIMR Office of Research Compliance (ORC) policies, the PIs are required to notify the ORC promptly of any unanticipated problems involving risks to subjects or others occur. The PIs will monitor the progress of the study and safety of participants on an ongoing basis. All serious AE (e.g., medical occurrences resulting in death) that occur during the study, defined by the given protocol, regardless of the relation to the research, must be reported to the ORC by telephone, e-mail, or fax within 24 hours of the investigator's awareness of the occurrence of the event. The PIs will report Serious Adverse Events (SAE) to the ORC, and will disseminate information to other agencies (e.g., NIOSH) as necessary. These initial reports are followed by a safety report, which is a written account of the serious AE determined by a sponsor/investigator to be both related to the treatment under investigation and to be unexpected in nature. Serious AEs will be summarized annually in the ORC application for continuation or termination of research.

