Aim 2: Participants will be given the taVNS unit to use at home by themselves for 8 weeks, regardless of treatment arm. They will be given the phone number for the project coordinator to contact if they have any questions or issues arise at any time. Additionally, during this window of 8 weeks, at the 4-week time point, the project coordinator will reach out, by phone, to check and see how the participant is doing, and assess if there are any issues. Adherence to the intervention will also be assessed through the device company's Nesos app, however this data

Protocol Number: 21-0640

February 1, 2022

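### The coordinator role that section 6.3 leaves unblinded also oversees the self-report surveys, and apparently makes the mid-treatment call and enters the biological data, with no stated safeguard

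*Protocol*

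**What the plan says.** Section 6.3 describes the trial as blinded for participants and all investigators, with one exception: "Only the research coordinators will not be blinded to the assignment". The exception follows from the logistics in the same section. "The coordinator will create and keep a crosswalk between participant ID, unique randomization ID number, and assignment in REDCap", and the coordinator then passes the table of IDs and assignments to the device company for programming. The list itself is generated "by a statistician not affiliated with the study".

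The coordinator also has these duties:

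- Surveys (6.3), in the words that run straight into that exception: "oversight of self-report survey completion will be provided by the research coordinator. Only the research coordinators will not be blinded to the assignment".
- Contact during home use (10.1.6): participants receive the project coordinator's phone number for questions or problems, and "at the 4-week time point, the project coordinator will reach out, by phone, to check and see how the participant is doing".
- Data entry (10.1.6, repeated in substance under its Data Management Plan and in 10.1.8.1): "Tracking and biological measures will be entered into REDCap by the project coordinator after each visit".

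Other steps lie elsewhere. Section 6.3 assigns the CAPS to senior study staff and the biological measurements to a separately named person. Section 6.1.1 has a research nurse draw blood and the app time-stamp each use. For the questionnaires, section 10.1.6 says: "Survey questionnaire responses will be entered directly into REDCap by responders from laptops or tablets provided at each visit".

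Section 4.1 calls the double-blind design important for limiting bias and says the pilot should reproduce the methods of the later trial.

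**The concern.** The bias-control section gives an outcome-facing task to the one role it declares unblinded. The protocol mentions no second, blinded coordinator, no scripted call and no restricted REDCap rights.

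Someone who knows the arm may, without intending to, encourage, troubleshoot or prompt differently. The outcomes within reach of that are:

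- **Primary:** retention, which Table 1 defines as completing the survey and biological measures at both visits, and adherence, which is logged automatically but is still behaviour that contact can change.
- **Secondary:** questionnaire time, item completeness, and the satisfaction score, whose goal is set in the intervention group.
- **Tertiary:** PCL-5, GAD-7, PHQ-9 and the sleep score, which feed the effect sizes for the future RCT (8.1, 9.3.1).

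A difference between taVNS and sham carried into planning could then partly reflect staff contact. The same staffing pattern could also pass into the larger trial.

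**Working it through.** **Step 1. Is it one role?** Section 6.3 says research coordinator; section 10.1.6 says project coordinator. Section 6.3 gives the coordinator the ID-to-assignment crosswalk, while sections 2.3.1 and 10.1.6 say only the project coordinator holds the link between identity and ID. One role is the natural reading, but the protocol never states it.

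**Step 2. When is the arm known?** Consent and enrolment take place at the fitting appointment (5.5). The coordinator receives the assignment after enrolment (6.3). Devices take about a month, and the baseline survey follows hand-over of the assigned device (6.1.1). On that sequence, both the baseline and the 8-week surveys are overseen by someone who knows the arm.

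**Step 3. What can the coordinator reach?**

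| Outcome | Produced by | Coordinator's route |
|---|---|---|
| CAPS | senior study staff | none stated |
| Biological measures | separately named person; nurse for blood | transcription |
| Device use | app log | phone line and 4-week call |
| Survey answers | participant | oversight of completion |
| Retention | both visits completed | survey oversight and contact |

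**Step 4. The plan's own precision figures.** With n = 30 and x = 30p, the Clopper-Pearson limits are Beta(0.025; x, n − x + 1) and Beta(0.975; x + 1, n − x). At the three expected rates:

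- 0.75: 0.559 to 0.889, width 0.330
- 0.80: 0.614 to 0.923, width 0.309
- 0.90: 0.735 to 0.979, width 0.244

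These match the table in section 9.2. They describe sampling error in the pooled sample only.

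**Step 5. Scale.** With 2:1 allocation, the arms are 30 × 2/3 = 20 and 30 × 1/3 = 10. Suppose, purely as an illustration, that contact makes two more taVNS participants adherent and one fewer sham participant.

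- taVNS: 2/20 = 10 points up
- Sham: 1/10 = 10 points down
- Difference between arms: 10 + 10 = 20 points
- Pooled rate: (2 − 1)/30 = 3.3 points

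The pooled estimate barely moves, while the contrast between arms moves a great deal. Each 10-point shift equals the gap between the two adherence figures in the protocol, 70% in section 8.1 and 80% in Table 1.

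For a continuous score with no dropout, the 95% half-width of the difference between arms is t(0.975, 28 df) × √(1/20 + 1/10) ≈ 0.79 SD. A contact effect smaller than that would lie within sampling error and could not be diagnosed from the results.

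**Step 6. Is the unblinding necessary?** Devices are labelled by randomization ID, and the company needs only that ID and the assignment (6.3). An unaffiliated statistician already generates the schema. Nothing in section 6.3 requires the table to pass through the person who deals with participants.

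**Step 7. Is the coordinator the only unblinded role?** Section 6.3 says so, but other sections point the other way. In 6.4, investigators check records against the randomization schema. In 7.2, a designated investigator has treatment status at all times. In 10.1.7, the principal investigator checks records against the randomization portal, although 6.3 says only the coordinator can access REDCap.

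**The case against.** The strongest reply is that the coordinator rates nothing. CAPS and biological measurement are done by others, use is time-stamped, participants key in their own answers, and section 10.1.6 plans verification by a second person or double entry. Instructions are the same in both groups (6.3), the app prompts sessions (6.2.4), and usage data are not to be used during the study (10.1.6). One scheduled call remains, plus any calls participants make. The primary precision basis is pooled, the by-arm summaries are descriptive, and section 9.3.1 promises caution with effect sizes.

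Most of this stands, and it rules out several stronger readings that a reader might infer:

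- That the trial is not double-blind where its endpoints are generated. The table in step 3 shows otherwise.
- That the coordinator is the participant's only contact during home use. Section 10.1.6 does not say so, and section 2.3.1 also directs participants to their provider if listed risks occur.
- That surveys are completed in the coordinator's presence. Section 6.3 says oversight only, and the synopsis allows an email link if COVID-19 restrictions require it.
- That the coordinators are in fact the only staff who can learn the assignment. Sections 6.4, 7.2 and 10.1.7 contradict this.

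The reply does not remove the remaining exposure. Verification catches transcription errors, not differential encouragement or prompting, and nothing stated in the protocol limits the latter.

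**Conclusion.** The point holds in a limited form. An unblinded coordinator has survey oversight and, if the two coordinator titles denote one role, participant contact and biological data entry. Self-report, satisfaction, completeness, retention and adherence could be influenced differently by arm. For the biological data the exposure is confined to transcription, which the planned verification addresses.

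The size and direction of any bias cannot be derived from the protocol. The shifts in step 5 show only how sensitive arms of 20 and 10 are, assuming full enrolment at exactly 2:1. The pooled feasibility rates are little affected. The consequence falls mainly on by-arm rates and on the effect sizes carried forward.

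This should be fixed because the fix is cheap, but it does not invalidate the pilot. Blinding the coordinator alone would not settle the matter while the investigators' access stays unreconciled.

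**What to change.** **Preferred.** In section 6.3, have the unaffiliated Biostatistics Unit statistician send the table of randomization ID and assignment directly to the device company. Restrict the REDCap assignment field so that the coordinator sees only the randomization ID, limit the coordinator's crosswalk to participant ID and randomization ID, and remove the sentence that leaves coordinators unblinded. Confirm first that the statistician's list carries the same IDs used on the device labels; section 6.3 says only that the schema is pre-generated and loaded into REDCap.

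**Alternative.** If the coordinator stays unblinded, move survey oversight, the phone line, the 4-week call and entry of biological measures to existing blinded staff.

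**In either case.** Leave emergency access to treatment status as section 7.2 has it. Reconcile sections 6.4, 7.2 and 10.1.7 with the statement in 6.3 that all investigators are blinded, naming who may see the assignment and for what purpose. Use one title for the coordinator throughout, or state that there are two roles.

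**Cost.** Protocol wording, a REDCap permission change, and either a small continuing task for the statistician over the 10 months of enrolment or a reallocation of duties among existing staff. No extra visits or participants are needed.
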